1.3.2. Secondary Efficacy Analysis

The secondary efficacy outcomes include:

- DDSS
- Itch questionnaires including diary WI-NRS, site WI-NRS and VRS
- Proportion of patients with improvement of WI-NRS \geq 4-point reduction;

- SCORAD;
- EASI;
- Proportion of patients with improvement on SCORAD index of at least 50%, 75% or 90% improvement.
- Proportion of patients with improvement on the EASI of at least 50%, 75% or 90% improvement.
- vIGA-AD;
- PGI-C;
- CGI-C;
- PBI-P;
- HRQOL-4;
- POEM;
- DLQI;
- ISQ;
- Pharmacokinetic-Pharmacodynamic correlation.

Continuous endpoints will be summarized and analyzed in a similar manner as the primary endpoint. Categorical endpoints will be analyzed by a Cochran–Mantel–Haenszel (CMH) test. Details of the analysis will be described in the SAP.

Time to event data will be analyzed using the Kaplan-Meier method, and the treatment group differences will be tested by the log-rank test. Details of the analysis will be described in the SAP.

1.4. Safety Data Analysis

The primary assessment of safety will be based on the frequency of treatment-emergent adverse events (TEAEs), serious adverse events (SAEs) and on the frequency of clinically notable abnormal vital signs, electrocardiograms (ECGs) and laboratory values. Other safety evaluations include changes in vital signs, changes in clinical laboratory evaluations, and changes in ECGs, physical exam findings during treatment, and suicide ideation (C-SSRS) and behavior events.

1.4.1. Adverse Events

Adverse events will be recorded throughout the study and at early discontinuation. Adverse events and medical conditions will be coded using the Medical Dictionary for Regulatory Activities (MedDRA) coding dictionary. Treatment-emergent adverse events will be defined as those events, which are newly occurring or worsening from baseline. In all cases only treatment emergent adverse events will be summarized.

Treatment-emergent adverse events will be summarized within each treatment group by primary system organ class and preferred term. (**NOTE:** In any given category [e.g. body system] a patient will only be counted once.) The incidence rates of TEAEs will be analyzed as described in the SAP. Similar displays will be provided for SAE and prior (conditions ending prior to the first dose of study medication) and current (conditions present while on study medication) medical conditions.

Adverse events will further be categorized by severity, relationship to study medication, and action taken. Other information collected will be listed, as appropriate. Any event starting more than 3 days after the final dose of study medication will be excluded from the above tables and only listed, unless the event caused discontinuation.

The proportions of patients experiencing SAEs and AEs resulting in discontinuation from the study will be summarized by treatment groups.

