1.2.3. Patient Disposition

Study completion and reasons for discontinuation for all randomized patients in the double-blind phase will be summarized for each treatment group. Discontinuations by reason will be tabulated by visit for each treatment group.

Time to discontinuation due to adverse events, lack of efficacy and for any reason will be analyzed using Kaplan-Meier survival techniques; the log-rank test will be used for group comparison.

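### The by-arm SAE display drops SAEs starting more than 3 days after the last dose unless they caused discontinuation, and the wording of the SAE proportions leaves unclear whether those events are counted by arm anywhere else.

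*SAP*

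**What the plan says.** All the operative text is in SAP section 1.4.1, apart from the statement of purpose in section 1.4.

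- Section 1.4 makes SAE frequency part of the main safety evaluation: "The primary assessment of safety will be based on the frequency of treatment-emergent adverse events (TEAEs), serious adverse events (SAEs" (the sentence goes on to vital signs, ECGs and laboratory values).
- Collection: "Adverse events will be recorded throughout the study and at early discontinuation".
- Definition: "Treatment-emergent adverse events will be defined as those events, which are newly occurring or worsening from baseline". A general limit is attached: "In all cases only treatment emergent adverse events will be summarized".
- After the TEAE tables by system organ class and preferred term, the section adds: "Similar displays will be provided for SAE".
- Next comes the exclusion: events with onset beyond "3 days after the final dose of study medication will be excluded from the above tables and only listed, unless the event caused discontinuation".
- A separate closing paragraph reads: "The proportions of patients experiencing SAEs and AEs resulting in discontinuation from the study will be summarized by treatment groups".

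**The concern.** A short post-dose window is an ordinary convention for an on-treatment table of non-serious events. Here it is also applied to the SAE display, and the only way back into the table is that the event caused discontinuation. Take a patient who stopped drug for another reason and then had a serious event, or died, more than 3 days later. That patient would not appear in the SAE display.

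This would matter little if another by-arm output clearly counted such patients. The obvious candidate is the closing sentence on SAE proportions, but it states no window and can be read in more than one way. SAE frequency is one of the quantities on which the primary safety assessment rests, so it should have one stated definition. Without one, the choice of what to count would be made when the tables are programmed or reported.

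**Working it through.** The plan gives no SAE rate or count to reproduce, so the check is mainly a reading of the text, followed by a statement of scale.

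**Step 1. Does the exclusion reach the SAE display?** Yes. The SAE display is announced before the exclusion, and the exclusion acts on the tables that precede it. The exclusion names any event and makes one exception, for discontinuation.

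**Step 2. Does the limit to treatment-emergent events remove late SAEs anyway?** No. The definition is anchored at baseline and has no end date. A serious event that starts well after the last dose is still newly occurring relative to baseline.

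**Step 3. What does the closing sentence on proportions count?** It comes after the exclusion, so it is not literally one of the tables covered. It also joins SAEs and AEs before the words about discontinuation, so those words may qualify one or both. Three readings follow. Here a late SAE means one that starts more than 3 days after the final dose and did not cause discontinuation.

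| Reading of the proportions sentence | Late SAE in the SAE display? | Late SAE in the proportions? | Consequence |
|---|---|---|---|
| A. All SAEs, no window | No | Yes | Late SAEs are counted by arm, but the two SAE figures can differ |
| B. All SAEs, 3-day cut carried over | No | No | The figures share a window; late SAEs are only listed |
| C. Only SAEs and AEs that led to discontinuation | No | No | The trimmed display is the only overall SAE count; late SAEs are only listed |

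The mismatch (A) and the missing count (B or C) are alternatives. They cannot both occur.

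**Step 4. Who can be affected?** Protocol Table 1 shows no visit after Visit 6, which also serves as the early-termination visit. On the scheduled visits, the exposed group is therefore mainly patients who stop drug more than 3 days before their last contact. Whether SAEs are also collected after the last visit, which would bring completers in, cannot be told from the supplied text.

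**Step 5. Scale.** Input: 175 patients per arm (SAP section 1.1), assuming that all are dosed and so belong to the Safety population.

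- One patient whose only SAE is late: 1/175 = 0.0057, or 0.57 percentage points of the arm.
- Illustration, with assumed counts: if 2 patients in an arm have an SAE inside the window, the display shows 2/175 = 1.14%. With 1 further patient whose only SAE is late, the figure without a window is 3/175 = 1.71%. With 3 such patients it is 5/175 = 2.86%.

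The documents give no SAE rate, dropout rate or interval between last dose and early-termination visit, so an expected number of late SAEs cannot be calculated.

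**The case against.** The case for leaving the text alone has four parts.

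*The full SAP may settle it.* SAP section 1.2 says that this text is general and that a complete description will follow in a SAP. Window footnotes usually belong there and in the table shells, and the SAE reporting period was not supplied either. This stands as a reason for modest confidence. However, what section 1.4.1 defers is how TEAE incidence is analysed. The 3-day exclusion is stated outright, so the point is more than missing detail.

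*The group is narrow.* A patient must be off drug for more than 3 days, still be under observation, and then have an SAE that does not itself cause discontinuation. Early leavers have a termination visit, and a prompt one shortens the exposed time further. This stands, and it is why the effect is probably small.

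*Deaths would be seen.* A death that itself ends participation plausibly meets the discontinuation exception. It would also appear in disposition, where section 1.2.3 says: "Discontinuations by reason will be tabulated by visit for each treatment group". This stands for such deaths. It does not help for a death, if recorded, in a patient already discontinued for another reason.

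*Nothing is lost.* Under reading A, the proportions are themselves the complete by-arm count. This is correct, but the text does not establish reading A.

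A reader might infer two stronger claims. One is that the plan will report two conflicting SAE figures. The documents do not support that as a general statement: it can happen only under reading A, and then only if a late SAE occurs. The other is that late SAEs disappear from the report. They do not, because the exclusion sends them to the listings.

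**Conclusion.** The point holds in a conditional form. As written, the SAE display omits late SAEs that did not cause discontinuation, with no exception for seriousness or death. Depending on how the next sentence is read, either a second SAE figure can differ from the display, or no by-arm adverse event summary counts those events.

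The size is probably small and cannot be quantified: up to 0.57 percentage points of an arm of 175 for each affected patient, with an unknown number of patients. Nothing supplied shows that the omission would favour either arm, and no efficacy result or planning figure is touched. The conclusion assumes that the full SAP does not already set the window, and that the SAE reporting period lets events more than 3 days after the last dose be recorded. This is a low-priority clarification, worth making because it costs little and concerns a stated component of the primary safety assessment.

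**What to change.** In section 1.4.1, or in the full SAP before database lock (SAP section 1.2 allows this without a protocol amendment):

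1. Exempt SAEs and deaths from the 3-day exclusion, so that all treatment-emergent SAEs recorded in the study are tabulated by arm.
2. State that the SAE proportions use the same window as that table.
3. Split the closing sentence into two outputs: 'patients with any SAE' and 'patients with any AE leading to discontinuation'.

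The 3-day window may stay for non-serious TEAEs. An on-treatment SAE table may also be kept if it is labelled as such.

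The cost is a wording change and one revised table, based on events that the study records in any case. The downside is that SAE counts may be slightly higher and include some events that arose off drug. A labelled on-treatment table would let a reader separate them.

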1.4.2. Laboratory Data

Clinical Laboratory Data

The summary statistics of raw data (hematology and chemistry) and change from baseline values will be presented, as well as shift tables from baseline to post-baseline values using normal ranges. For urinalysis parameters, the number and percentage of patients falling under each category of the test will be presented.

Clinical laboratory data will be summarized for each treatment group by presenting the proportions of patients with clinically notable abnormalities ([Appendix 22.1](#)).

Clinically notable values will be identified according to the criteria identified in the FDA's "Supplementary Suggestions for Preparing an Integrated Summary of Safety Information in an Original NDA Submission and for Organizing Information in Periodic Safety Updates" (Revised 2-APR-87) provided by the FDA Division of Neuropharmacological Drug Products (DNDP). Differences in incidence rates between the treatment groups will be tested as described in the SAP.

1.4.3. Vital Signs and Body Measurements

Data from vital signs and body measurements will be listed, clinically notable values ([Appendix 22.1](#)) will be flagged, and any other information collected will be listed. Data will also be summarized by treatment group using mean change from baseline and proportions of patients with values outside the normal range, and values that were clinically notable.

1.4.4. Electrocardiogram (ECG)

Results from the ECG will be listed for each patient. These data will also be summarized for each treatment group by presenting patients with newly occurring or worsening ECG abnormalities.

1.4.5. Columbia-Suicide Severity Rating Scale (C-SSRS)

Results from the C-SSRS will be listed for each patient. These data will also be summarized by treatment group and for suicidal ideation events, suicidal behaviors and completed suicides. In particular, for each of the following suicide related events, the number and percent of patients with the event will be enumerated by treatment group: completed suicide, nonfatal suicide attempt, interrupted attempt, aborted attempt, preparatory acts or behavior, active suicidal ideation with specific plan and intent, active suicidal ideation with some intent to act without specific plan, active suicidal ideation with any methods (no plan) without intent to act, non-specific active suicidal thoughts, and wish to be dead. Details of the analysis will be provided in the SAP.

1.5. Subgroup Analysis

The subgroup analysis (such as, sex, age, baseline illness severity etc.) for efficacy variables and safety variables may be conducted as described in the SAP.

1.6. Interim Analysis

No interim analyses are planned.

1.7. Deviations in Analysis from Statistical Plan and Other Issues

During the analysis and reporting process, any deviations from the statistical plan designed for this protocol will be described and justified in the final report.
